6.8 Recommended treatment of adverse events

Treatment of AEs should follow standard practice. Medication used to treat AEs must be recorded on the Concomitant medications/Significant non-drug therapies CRF.

6.9 Rescue medication

Use of rescue medication must be recorded on the Concomitant medications/Significant non-drug therapies CRF after start of study drug. Additional doses of LFG316 may be administered in case of hemolytic crisis between infusions (as evidenced e.g. by sudden increase in LDH levels, decrease in Hb and based on Investigator's judgment, and can be discussed with Novartis).

Use of eculizumab or other biologics as a rescue medication would lead to treatment discontinuation, and subjects entering the 8 week safety follow-up. Blood transfusions and other therapeutic measures are permitted, as outlined in [Section 6.1.2](#).

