1.2 Study purpose

The purpose of the study is to determine whether LFG316 administered via i.v. infusion at 20 mg/kg once every 14 days can induce a hematological response, as measured by reduction in hemolytic activity, in patients with PNH. Commercially Confidential Information

Period 3 (extension of treatment duration) was implemented to ensure a seamless continuation of treatment for LFG316-responsive patients enrolled in the study.

Period 4 is implemented to convert PNH patients receiving i.v. infusion of LFG316 to oral treatment with LNP023, thereby allowing them to be considered for participation in the planned long-term extension study CLNP023C12001B.

2 Study objectives

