3.1 Study design

This is an open-label, non-controlled study in patients with PNH. Approximately 10 patients will be enrolled in the study. At the time that Protocol amendment v07 is effective, no additional patients will be enrolled. The study drug will be administered via i.v. infusion at the dose level of 20 mg/kg every 14 days. Patients participating in study will have an option to either complete period 3 Follow up and Study Completion evaluation or continue in study period 4 that is pre-requisite to join the long-term extension study CLNP023C12001B, that is separate to this study protocol. Patients who are potentially eligible and willing to participate in the LNP023 long-term extension study will join period 4, where treatment will be converted from LFG316 to LNP023 200 mg b.i.d.

The study will consist of a 60-day screening period to assess eligibility and conduct vaccinations if required (for all patients not previously vaccinated at least 2 weeks prior to first dosing or if prior vaccination cannot be confirmed). An extensive screening window (up to 60 days) is planned in order to comply with local vaccination requirements, if available and deemed necessary at the investigator's discretion. Safety evaluation assessments requiring blood and urine samplings, pregnancy test, pulmonary function test, ECG, patient reported outcomes, and assessment of number of blood transfusions should be performed no longer than 4 weeks prior

to the planned dosing day. Subjects who meet the eligibility criteria at screening will be admitted to baseline (Day 1) evaluations. The patients will enter treatment period 1, and will receive infusions of LFG316 every 14 days, days 1, 15 and 29 (3 administrations).

At the end of period 1, efficacy on hemolytic activity by serum LDH will be assessed. All patients will then be allowed to enter the optional treatment period 2, and will receive infusions of LFG316 every 14 days, and undergo the efficacy, PK, CCI and safety assessments for additional 48 weeks.

Following the 48-week treatment period 2, LFG316-responsive patients (assessed based on investigator's judgment) will be allowed to enter an additional third extension period of up to 260 weeks (extension period 3).

The LFG316 treatment for all patients will be completed by end of 2021 regardless of each individual treatment period.

[figure not shown]

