6.1.2 Additional study treatment

Permitted concomitant medications are listed below:

- Erythropoietin
- Corticosteroids and/or other immunosuppressive regimens may be continued throughout if warranted for treatment of autoimmune disease (e.g. aplastic anemia). It is strongly recommended, but is at the investigator's discretion, that patients receive appropriate prophylactic antibiotics (e.g. ciprofloxacin, penicillin, erythromycin) while on treatment with any type of concomitant immunosuppressive agent other than LFG316 (including corticosteroids)
- Anticoagulants, e.g. coumarins, low molecular-weight heparins, factor Xa inhibitors, Thrombin inhibitors
- Iron supplements & folic acid
- Iron depletion therapy as required
- Blood transfusions as required
- Analgesic agents
- Antibiotics, antivirals

Any dose adjustments or new concomitant treatments must be recorded in the relevant eCRF page.

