11.4.1 Variable(s)

The primary efficacy variable for assessing the effect of LFG316 over the first 4 weeks of treatment is response rate where a patient will be considered a responder if the percentage reduction from baseline in serum LDH is at least 60% at any time up to and including week 4 for that patient.

The primary efficacy variable for assessing the effect of LFG316 over the entire treatment period is the actual serum LDH value measured at multiple time points during the study.

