11.4.2 Statistical model, hypothesis, and method of analysis

Proof of concept will be based on LDH levels during the first four weeks. A positive sign of efficacy is when:

- The estimated median response rate is at least 50%

Commercially Confidential Information

For the analysis of serum LDH values from multiple time points, a longitudinal model analysis of log-transformed LDH levels over time pre- and post-treatment will also be performed.

Longitudinal modelling will include individual and treatment average graphical presentations over time incorporating any historical LDH data collected so as to better put post-treatment changes in context.

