11.4.3 Handling of missing values/censoring/discontinuations

The study aims to replace subjects enrolled before protocol amendment 5 who discontinue before the end of period 1 for reasons other than safety and the primary responder analysis will be based on period 1 completers only, in a per protocol fashion.

Further longitudinal model analyses performed to assess the effect of missing data on the conclusions drawn from the primary analysis will include, if available, data from any subjects who discontinued early. Lack of efficacy will not be considered a missing value. Even if treatment is discontinued, LDH values should still be assessed in the eight-week follow-up period.

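### The week-4 responder rule sets no visible condition on rescue, so a 60% LDH fall first reached after an extra LFG316 dose counts as response to the 14-day regimen

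*Protocol*

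**What the plan says.** **Question.** Protocol 1.2 asks whether LFG316 "administered via i.v. infusion at 20 mg/kg once every 14 days can induce a hematological response" in PNH. The primary objective in Protocol 2.1 and SAP 2.1.1 is broader: the effect of LFG316 on intravascular hemolysis, with no regimen named.

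**Endpoints.** Under Protocol 11.4.1 and SAP 7.1.1 a patient responds if the "percentage reduction from baseline in serum LDH is at least 60% at any time up to and including week 4". The second primary variable, for the whole treatment period, "is the actual serum LDH value measured at multiple time points during the study". The visible proof-of-concept criterion in Protocol 11.4.2 and SAP 7.1.3 is: "The estimated median response rate is at least 50" (per cent). Section 3.1 gives the size: "Approximately 10 patients will be enrolled in the study".

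**Rescue.** Protocol 6.9, under the heading of rescue medication, says: "Additional doses of LFG316 may be administered in case of hemolytic crisis between infusions". Treatment then continues. Eculizumab or another biologic used as rescue ends treatment and starts the 8-week follow-up. Section 6.1.2 permits "Blood transfusions as required". Section 3.3.1 allows the regimen to be adjusted in period 2, with breakthrough hemolysis as an example, but in period 1 only where safety makes it unavoidable. Section 6.3 also discourages adjustment in period 1.

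**Incomplete data.** Protocol 11.4.3 and SAP 7.1.5 restrict the responder analysis to patients who complete period 1. Both say that lack of efficacy is not to be treated as missing. Protocol 11.4.3 brings early discontinuers into further longitudinal models and adds: "Even if treatment is discontinued, LDH values should still be assessed in the eight-week follow-up period". Section 11.3 names rescue medication in its heading, but its text only lists and summarizes study drug and concomitant therapy.

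**The concern.** The responder rule takes the best LDH value to week 4 and does not ask what was given before it. Consider a patient who has a hemolytic crisis between scheduled infusions, receives an extra dose, and only then falls 60% below baseline. That patient is a responder, although the scheduled regimen alone had not produced the response. The patient also stays on treatment, so the restriction to completers does not remove the case.

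Eculizumab rescue raises a related problem. It ends treatment, so a patient for whom LFG316 failed in period 1 can disappear from the responder analysis instead of counting as a failure.

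For the longitudinal analyses, LDH measured on eculizumab during follow-up can be included through the early discontinuers, and no cut-off is visible. At stake is whether the proof-of-concept result answers the question in Protocol 1.2.

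**Working it through.** **The plan's own figure.** The enrolment of about 10 cannot be reproduced. The sample-size text in Protocol 11.6, the prior, and anything beyond the first proof-of-concept criterion are redacted. The priors, true rates and conversion shares below are assumptions.

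**1. Direction.** Let S be a patient's LDH values before the first extra dose and T all values to week 4. S is part of T, so min(T) ≤ min(S). Anyone who reaches a 60% fall within S also reaches it within T. Using T in place of S can therefore add responders and cannot remove one.

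**2. Where the visible rule turns.** With x responders of n and a Beta(a, b) prior, the posterior is Beta(x + a, n − x + b), and its median is compared with 0.50.

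| Prior | Median at 4/10 | Median at 5/10 |
|---|---|---|
| Beta(1, 1) | 0.412 | 0.500 |
| Beta(0.5, 0.5) | 0.403 | 0.500 |
| Beta(1/3, 1/3) | 0.400 | 0.500 |

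Four responders fail and five pass, so one patient can decide the result.

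**3. How often one conversion is decisive.** Exactly four of the ten must otherwise respond:

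- True rate 40%: 210 × 0.4^4 × 0.6^6 = 0.251.
- True rate 70%: 210 × 0.7^4 × 0.3^6 = 0.037.

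These are ceilings for a single conversion. The conversion must also occur: no 60% fall yet, a crisis, an extra dose despite the caution in Sections 3.3.1 and 6.3, then a 60% fall by week 4.

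**4. If conversions were a steady share.** Let p be the true rate without rescue and q the share of non-responders who become responders after an extra dose. The counted rate is p + (1 − p)q. For p = 0.40 and q = 0.10 it is 0.40 + 0.60 × 0.10 = 0.46. The chance of at least 5 of 10 is then:

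| p | q = 0 | q = 0.10 | q = 0.20 | q = 0.30 |
|---|---|---|---|---|
| 0.30 | 0.150 | 0.294 | 0.470 | 0.647 |
| 0.40 | 0.367 | 0.522 | 0.671 | 0.798 |
| 0.50 | 0.623 | 0.738 | 0.834 | 0.905 |

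The q = 0 column is what results when rescued patients are scored as non-responders. The documents give no basis for any particular q.

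**5. Eculizumab and the denominator.** Take 10 dosed patients with 4 responders, where k non-responders leave through eculizumab in period 1 and are not replaced. The medians use the flat prior.

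| k | Completers' rate | Median | All dosed |
|---|---|---|---|
| 1 | 4/9 = 44% | 0.452 | 4/10 = 40% |
| 2 | 4/8 = 50% | 0.500 | 4/10 = 40% |
| 3 | 4/7 = 57% | 0.560 | 4/10 = 40% |

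Two such exits are enough to meet the visible bar. Replacement, which the plan aims for in some patients, would refill the denominator but would not bring the failures back.

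**6. Longitudinal data.** Three statements in Protocol 6.9 and 11.4.3 combine: eculizumab leads to 8 weeks of follow-up, LDH is still measured then, and further models include early discontinuers. Values on eculizumab can therefore enter those models. Nothing visible cuts or labels them.

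**The case against.** **Redaction.** Text is removed from Protocol 6.3, 11.1, 11.4.2 and 11.4.4 and from SAP 5, 7.1.3 and 7.1.6, and a rule could sit there. This stands as a caveat. The definitions and missing-data text in Protocol 11.4.1 and 11.4.3 and SAP 7.1.1 and 7.1.5, the natural places for such a rule, show no redaction and contain none.

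**An extra dose is still LFG316.** Under the objective in Protocol 2.1, counting all values on LFG316 is a legitimate treatment-policy choice. That also stands. The conflict is with the regimen named in Section 1.2, and the plan does not say which question the responder rate answers.

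**Few events.** Period 1 is short and dose changes are discouraged, so a decisive case is likely to be uncommon. Agreed.

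A reader might also infer more than the documents support:

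- *That a fall on eculizumab counts as response.* In period 1 the drug ends treatment and the analysis uses completers, so the patient is dropped, not credited.
- *That LDH on eculizumab is modelled as LFG316 effect.* It can enter the further longitudinal models, but their terms are not visible, and SAP 7.1.6 makes longitudinal modelling conditional on its being thought useful.
- *That the bias always favors LFG316.* This holds for admitting post-rescue values under the responder rule. In longitudinal data, LDH that rises again off drug in patients without a replacement inhibitor would count against LFG316.
- *That transfusion produces false responses.* No passage says that transfusion lowers LDH.
- *That the chance of at least one rescue measures the chance of a changed result.* With an assumed 5%, 10% or 20% event rate, 1 − (1 − rate)^10 is 40%, 65% or 89%. That is the chance of any event; conversion and a decisive count are further conditions.

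**Conclusion.** The point holds for the responder rate. In the visible text, a 60% fall first reached after an extra LFG316 dose counts towards the 14-day regimen, and admitting such values can only raise the count. One patient separates 4/10 from 5/10 under the three assumed priors. A single conversion decides the outcome with probability at most 0.251 at an assumed true rate of 40%, and 0.037 at 70%.

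Eculizumab in period 1 is a separate gap that acts through exclusion: two such non-responders leaving turn 40% into 50%. The statement that lack of efficacy is not missing data suggests that these patients should count as failures, but the restriction to completers points the other way, and the text does not settle it.

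For the longitudinal analyses the finding is limited to a missing cut-off, with no fixed direction of bias. All of this assumes that no rule sits in redacted text. The issue is worth settling in the SAP because a rare event can decide so small a trial, not because the result is shown to be wrong.

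**What to change.** Change the analysis rules only; clinical management stays as it is.

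1. **Responder analysis (SAP 7.1.1 and 7.1.5).** Score a patient who receives an extra LFG316 dose or another complement inhibitor before first reaching a 60% fall as a non-responder. Keep such patients in the denominator even if they do not complete period 1.
2. **Sensitivity.** Repeat the responder analysis with all observed LDH values. An analysis around transfusions is optional.
3. **Longitudinal analyses of LFG316.** Cut LDH at the first dose of another complement inhibitor, and flag off-drug values and values after a regimen change. The separate presentation of period 4 is unaffected.
4. **If a redacted section already holds such a rule,** refer to it from SAP 7.1.1 and 7.1.5.

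Protocol 6.9 and 6.10 already require rescue medication and transfusions to be recorded, and study drug administration is to be listed under 11.3, so no new data are needed. The cost is SAP wording, one extra run, and possibly a slightly lower reported response rate.

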6.10 Concomitant treatment

All prescription medications, over-the-counter drugs and significant non-drug therapies (including physical therapy and blood transfusions) administered or taken within the timeframe defined in the entry criteria prior to the start of the study and during the study, must be recorded on the Concomitant medications/ Significant non-drug therapies section of the CRF.

Medication entries should be specific to trade name, the single dose and unit, the frequency and route of administration, the start and discontinuation date and the reason for therapy.

7 Discontinuation and study completion

7.1 Discontinuation of study treatment

Subjects may voluntarily discontinue study treatment for any reason at any time.

The investigator must discontinue study treatment for a given subject if, on balance, he/she believes that continuation would be detrimental to the subject's well-being.

Study treatment must be discontinued under the following circumstances:

- Subject withdraws consent
- Pregnancy
- Emergence of the following adverse events:
 - Evidence for invasive Neisseria infection
 - In case of other severe systemic or life-threatening infections, treatment discontinuation should be decided on a case-by-case basis

- Use of prohibited treatment as per [Section 5.2](#).
- Any other protocol deviation that results in a significant risk to the subject's safety

Subjects who discontinue study treatment or who decide they do not wish to participate in the study further should NOT be considered withdrawn from the study UNLESS they withdraw their consent (see [Section 7.3](#)). Where possible, they should return for the 8 week safety follow-up, which includes monitoring of intravascular hemolysis after drug discontinuation. If they fail to return for these assessments for unknown reasons, every effort (e.g. telephone, e-mail, letter) should be made to contact them as specified in [Section 7.2.1](#).

If treatment with LNP023 has to be discontinued prematurely and immediately (i.e., because of a significant safety risk which warrants immediately stopping LNP023 treatment), it is recommended to promptly re-initiate treatment with Standard of Care (SoC), as judged by the investigator.

Close monitoring of patients for signs and symptoms of hemolysis should be performed upon LNP023 discontinuation. It is recommended to monitor at minimum for: increase in LDH, decrease in hemoglobin level and PNH clone size, increase in serum creatinine, thrombosis, and change in neurological/mental status. If serious hemolysis occurs, the Investigator should consider the following supportive treatments (and recording them in the appropriate CRF pages):

- Blood transfusion (packed RBCs), or
- Exchange transfusion if the PNH RBCs are >50% of the total RBCs by flow cytometry,
- Corticosteroids,
- Anticoagulation,
- Any other supportive treatment or therapy as judged by the investigator.

An End of Study (EoS) visit one week after permanent discontinuation of LNP023 should occur for the assessments as specified in the [Assessment schedule](#).

If treatment with LNP023 has to be discontinued prematurely but it is not warranted to immediately discontinue LNP023 treatment (i.e., discontinuation due to patient/guardian decision or confirmed pregnancy), it is recommended to promptly initiate the available SoC in the country as judged by the investigator. In addition, it should be considered to taper down LNP023 over a period of 14 days:

Commercially Confidential Information

Down-titration is also recommended for patients who start LNP023 treatment in period 4 and do not join long-term extension study.

The investigator should consider the proposed monitoring and supportive treatments listed above in case serious hemolysis occurs. During LNP023 tapering, weekly visits are recommended

Commercially Confidential Information

The following assessments are recommended: blood hematology and chemistry for parameters specified in [Section 8.3.4](#).

All data collected will be entered in the appropriate CRF page as an unscheduled visit/assessment.

7.2 Study completion and post-study treatment

Each subject will be asked to complete this study in its entirety (period 1, 2 and 3) and they may be offered to enter an additional extension trial, provided LFG316 shows benefit as defined by the response criteria. Patients willing and eligible to join the extension study CLNP023C12001B must participate in period 4.

Study completion is defined as when the last subject completes their End of Study visit, and any repeat assessments associated with this visit have been documented and followed-up appropriately by the Investigator, or in the event of an early study termination decision, the date of that decision.

At a minimum, patients ending participation after period 3, will be contacted for safety evaluations during the 8 week safety follow-up period in which intravascular hemolysis will be monitored, and a final Study Completion Visit will be conducted at the conclusion of the safety follow-up period. A safety follow-up call should be conducted approximately 30 days after last LNP023 administration to confirm the patient has not experienced any SAEs during this post-study period for any patient participating in period 4, who does not roll over into CLNP023C12001B. Documentation of attempts to contact the subject should be recorded in the source documentation. The investigator must provide follow-up medical care for all subjects who are prematurely withdrawn from the study, or must refer them for appropriate ongoing care.

7.2.1 Lost to follow-up

For subjects whose status is unclear because they fail to appear for study visits without stating an intention to discontinue or withdraw, the investigator should show "due diligence" by documenting in the source documents steps taken to contact the subject, e.g. dates of telephone calls, registered letters, etc. A subject should not be formally considered lost to follow-up until his/her scheduled end of study visit would have occurred.

7.3 Withdrawal of consent

Subjects may voluntarily withdraw consent to participate in the study for any reason at any time.

Withdrawal of consent occurs only when a subject does not want to participate in the study anymore **and** does not allow further collection of personal data.

If a subject withdraws consent, the investigator must make every effort to determine the primary reason for this decision and record this information. Study treatment must be discontinued and no further assessments conducted, and the data that would have been collected at subsequent visits will be considered missing. Further attempts to contact the subject are not allowed unless safety findings require communicating or follow-up.

Novartis will continue to keep and use collected study information (including any data resulting from the analysis of a subject's samples until the time of withdrawal) according to applicable law.

For US and Japan: All biological samples not yet analyzed at the time of withdrawal may still be used for further testing/analysis in accordance with the terms of this protocol and of the informed consent form.

For EU and RoW: All biological samples not yet analyzed at the time of withdrawal will no longer be used, unless permitted by applicable law. They will be stored according to applicable legal requirements.

